8.5.2.5 Coagulation parameters

- Fibrinogen
- Prothrombin time (PT) including INR
- D-dimer
- Prothrombin fragment 1+2
- Activated partial thromboplastin time (APTT)
- Antithrombin (AT)

The investigator must evaluate the results and record the outcome as:

- Normal or abnormal
- If abnormal the investigator must:
 - Specify the abnormality
 - Record if the result is clinically significant (Yes/No)
 - If observed before or at screening: record as concomitant illness (section [8.2.2](#))
 - If observed after screening: report an AE/SAE (section [12](#))

Protocol
 Trial ID:NN7415-4255
 UTN:U1111-1179-3872
 EudraCT no.:2016-000614-29

~~CONFIDENTIAL~~

Date:	05 May 2017	Novo Nordisk
Version:	2	
Status:	Final	
Page:	66 of 124	

8.5.2.6 FVIII inhibitor test

The inhibitor level of the patient will be measured by the Nijmegen method at visit 1 (screening).

- FVIII inhibitor titre (BU)

8.5.2.7 Anti-concizumab antibodies

Sampling will be performed at all visits except at visit 3. Samples will be collected pre-dose at visit 2, 9 and 16.

Assessment of binding antibodies against concizumab (anti-drug antibodies (ADA)) will be performed at specialised laboratories whereas assessment of neutralising antibodies will be performed at Novo Nordisk A/S.

Analysis for ADA will be done as listed in [Table 2-1](#), with a bridging ECL assay (binding ADA assay), using labelled concizumab for antibody capture and detection. Confirmed positive samples will be characterised for binding to IgG backbone, CDR region or the S241P mutation. Furthermore, positive samples will be characterised for neutralising activity using a modified TFPI functionality assay (neutralising ADA assay). All antibody assays are validated according to international guidelines and recommendations.

The following analyses will be available:

- Anti-concizumab antibody assay
- Specificity assay (Anti-concizumab antibodies cross reacting with IgG4 backbone, CDR region or S241P mutation)
- Anti-concizumab neutralising antibody assay

Samples will be drawn at all visits except at visit 3. The samples will be analysed in batches during the trial and results will be available to the data monitoring committee approximately every third month after the first patient has been dosed (Section [12](#)). Neutralising antibodies will be analysed and reported at the end of trial. A detailed description of the assay methods will be included in the antibody analysis report at the end of the trial.

Investigators will be notified in case their patient is shown to have developed neutralising antibodies against concizumab.

Samples for the determination of anti-drug antibodies collected during the treatment period must be drawn prior to administering trial products.

In the event that a trial patient develops binding ADAs towards concizumab during the course of the trial and has measurable binding ADAs at his End of Trial visit, the patient may attend an ADA follow-up visit. The ADA positive patients will be called for additional visits, e.g. every 4 to 6 weeks, for safety assessment and blood sampling for ADA and PD markers (free TFPI and

Protocol
 Trial ID:NN7415-4255
 UTN:U1111-1179-3872
 EudraCT no.:2016-000614-29

~~CONFIDENTIAL~~

Date:	05 May 2017	Novo Nordisk
Version:	2	
Status:	Final	
Page:	67 of 124	

Thrombin generation). The ADA positive patients will be followed no longer than one year after End of Trial.

Hypersensitivity

If suspicion of a hypersensitivity reaction occurs, patients should be instructed to contact the site staff as soon as possible for further guidance, see Section [12.1.5](#).

In the event of a severe local and/or systemic hypersensitivity reaction possibly or probably related to trial product, blood sampling for assessment of anti-concizumab IgE antibodies as well as anti-concizumab antibodies should be conducted in relation to the reaction and no later than 1-2 weeks after the event. Additional testing may be performed if deemed relevant (e.g. anti-Host Cell Proteins (HCP) antibodies).

In the event of a severe systemic hypersensitivity reaction to trial product it is recommended also to test for tryptase (total and/or mature tryptase) within 3 hours of the reaction. Moreover, a baseline tryptase measurement is necessary 1-2 weeks after the immediate severe hypersensitivity reaction due to individual to individual variation in tryptase baseline concentration.

A follow up visit should be conducted 3-4 weeks post the allergic reaction with repeated blood sampling for assessment of anti-concizumab IgE antibodies as well as anti-concizumab antibodies and if possible also at a visit 3 months post the hypersensitivity reaction for assessing the persistence of the IgE response. Tryptase measurements are not required at the follow up visits.

Additionally, basophil activation testing may be performed if deemed relevant. This can be performed using existing samples and/or by analysing the patient's basophil cells from an additional blood sample taken 3-4 weeks and no later than 2 months after the event. Similarly, prick tests and/or intra-dermal tests may be performed if relevant using trial product or components of trial product. Complement may be measured in case of suspicion of immune complex mediated hypersensitivity reactions.

Results from the following additional tests will be reported to Novo Nordisk Safety Operations for inclusion in the ARGUS database and included in the narratives, if measured:

Test to be performed in case of severe hypersensitivity

- Anti-concizumab IgE antibodies
- Anti-concizumab antibodies (additional to scheduled time points)

Additional testing may be performed if deemed relevant e.g

- Anti-Host Cell Proteins (HCP) antibodies
- Anti-HCP IgE antibodies
- Basophil activation results

Protocol
Trial ID:NN7415-4255
UTN:U1111-1179-3872
EudraCT no.:2016-000614-29

~~CONFIDENTIAL~~

Date: 05 May 2017
Version: 2
Status: Final
Page: 68 of 124

Novo Nordisk

- Prick test/intra-dermal test
- Complement test results

Furthermore, it is recommended locally to test for

- Tryptase (total and/or mature tryptase)

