6.4 Criteria for premature discontinuation of trial product

The patient may be prematurely discontinued from trial product at the discretion of the investigator due to a safety concern.

The patient must be prematurely discontinued from trial product if the following applies:

1. Included in the trial in violation of the inclusion and/or exclusion criteria
2. Simultaneous participation in another clinical trial of an approved or non-approved investigational medicinal product.
3. Incapacity or unwillingness to follow the trial procedures
4. Anaphylactic reaction
5. Thromboembolic event
6. Event of disseminated intravascular coagulation (DIC)
7. Development of inhibitors to Factor VIII (≥ 0.6 BU)
8. Lack of efficacy due to neutralising antibodies towards concizumab
9. Lack of efficacy defined as ≥ 3 treated sBEs within the previous 12 weeks in patients being treated with the highest dose level (0.25 mg/kg) of concizumab.

See Section [8.1.4](#) for procedures to be performed for patients discontinuing trial product prematurely.

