6.7 Rationale for trial population

The most important reason for choosing the trial population, haemophilia A without inhibitors, is that there is a significant unmet medical need in this patient population for a treatment option which reduces the burden associated with the current care, including small volume s.c. administration instead of i.v. Finally, the trial population reflects the patient population that will be selected in a potential subsequent phase 3 trial in which the efficacy and safety of concizumab is to be confirmed.

Protocol
 Trial ID:NN7415-4255
 UTN:U1111-1179-3872
 EudraCT no.:2016-000614-29

~~CONFIDENTIAL~~

Date:	05 May 2017	Novo Nordisk
Version:	2	
Status:	Final	
Page:	40 of 124	

7 Milestones

Planned duration of recruitment period first patient first visit – last patient first visit (FPFV-LPFV):
 4 months

Planned FPFV:	16-Aug-2017
Planned FPFT:	30-Aug-2017
Planned LPFV:	16-Dec-2017
Planned LPLV:	11-Sep-2019

The total duration of concizumab treatment in the trial is 76 weeks for an individual patient enrolled in the trial for concizumab treatment at visit 2.

End of trial is defined as last patient last visit (LPLV).

Recruitment:

The screening and enrolment rate will be followed closely via the interactive web response system (IWRS) in order to estimate when to stop screening. All investigators will be notified immediately when the recruitment period ends, after which no further patients may be screened and the IWRS will be closed for further screening. All patients screened during the recruitment period and found eligible for enrolment can be enrolled within the timelines specified in the flow chart (see Section [2](#)).

Trial registration:

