8.1.11 Follow-up Part

8.1.11.1 Visit 17 (End of trial)

Visit 17 is to be scheduled on trial day 589 (84 weeks) with a visit window of minus 7 days

Assessments are to be performed according to [Table 2–1](#) and the assessment results from concomitant medication, physical examination, body measurements (weight only), vital signs and details of adverse events must be entered into the eCRF.

Investigator is to perform compliance check of treatment and reporting of bleeding episodes through reviewing collected data from the eDiary. Patients must be asked if their female partner has become pregnant during the trial (see Section [12.5.1](#)).

The patient will be asked to return all used, partly used and unused turoctocog alfa (rFVIII), eDiary device and Trial card. Drug accountability must be performed for turoctocog alfa (rFVIII) including injection kits, if applicable.

End of trial information must be entered in the End of Trial form in the eCRF.

End of trial Call must be made in the IWRS.

Protocol
 Trial ID:NN7415-4255
 UTN:U1111-1179-3872
 EudraCT no.:2016-000614-29

~~CONFIDENTIAL~~

Date:	05 May 2017	Novo Nordisk
Version:	2	
Status:	Final	
Page:	52 of 124	

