8.5 Laboratory assessments

An approximate total blood volume of 450 mL will be taken from each patient in the trial. Ports cannot be used for blood sampling.

A laboratory manual will be provided for detailed description of obtaining and processing blood samples.

All laboratory blood samples collected for this trial except for haematology samples are to be shipped for analysis at central laboratories or further distribution to special laboratories. Haematology samples are to be analysed locally.

The laboratory provides results to the trial sites in the units preferred by the trial sites while the results that are transferred to the trial database will always be in international system of units (SI).

Laboratory reports listing results from centrally analysed samples will be made available for the investigator. Investigator must review and evaluate the results and report AEs for results which are clinically significant. Laboratory reports will where possible indicate normal ranges

Categorisation of clinical significance for out of range results may not be required for the following laboratory parameters and the investigator is therefore not required to perform a categorisation even though these parameters are listed in the laboratory report: FVIII activity, FVIII inhibitor test, Thrombin generation, TFPI not bound to concizumab, concizumab concentration in plasma, Anti-concizumab binding antibodies, and Total TFPI.

The laboratory equipment may provide analyses not requested in the protocol but produced automatically in connection with the requested analyses according to specifications in the laboratory standard operating procedures. Such data will not be transferred to the trial database, but abnormal values will be reported to the investigator. The investigator must review all laboratory results for concomitant illnesses and AEs and report these according to section [8.2.2](#) and section [12](#).

Only laboratory samples specified in the protocol must be sent to the central laboratory for analysis; if additional laboratory sampling is needed, e.g. to follow up on AEs, this must be done at a local laboratory except for biomarkers and anti-drug antibodies (anti-concizumab IgE antibodies and anti-concizumab binding antibodies).

Laboratory samples will be destroyed no later than at finalisation of the clinical trial report (CTR).

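### Stopping for lack of efficacy due to neutralising anti-concizumab antibodies is mandatory, but the neutralising assay is scheduled for the end of trial, so no scheduled result exists while a patient is dosed

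*Protocol*

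**What the plan says.** All references are to protocol version 2 (5 May 2017).

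- **Section 6.4, item 8** is in the list of criteria under which trial product must be stopped: "Lack of efficacy due to neutralising antibodies towards concizumab". It names no assay and no bleed threshold.
- **Section 6.4, item 9** forces a stop at three or more treated spontaneous bleeds within 12 weeks, but only at 0.25 mg/kg.
- **Section 8.5.2.7** has antibody samples analysed in batches during the trial, with results to the DMC about every three months. The next sentence treats neutralising antibodies separately: "Neutralising antibodies will be analysed and reported at the end of trial". The binding assay runs at specialised laboratories, while "assessment of neutralising antibodies will be performed at Novo Nordisk A/S".
- **Section 8.5.2.7** also states: "Investigators will be notified in case their patient is shown to have developed neutralising antibodies against concizumab". No time is given.
- **Section 7** equates end of trial with last patient last visit (LPLV). Section 8.5.2.7 also uses the term for the individual patient, who may be followed further if he "has measurable binding ADAs at his End of Trial visit". Section 8.1.11.1 fixes that visit: "Visit 17 is to be scheduled on trial day 589 (84 weeks) with a visit window of minus 7 days". The last dose is at visit 16, day 533 (section 8.1.10.3).
- **Table 2-2, footnote m** allows extra antibody samples after clinical signs. It gives hypersensitivity and immune-related events as examples, and has the affected patient's antibody samples analysed as the trial proceeds.
- **Section 5.3.1** escalates a patient with three or more treated spontaneous bleeds in 12 weeks from 0.15 to 0.20 and from 0.20 to 0.25 mg/kg. This applies if the investigator deems it safe after weighing the clinical picture and available laboratory results. Bleeds are counted afresh at each new level.

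**The concern.** Item 8 turns on the cause of the lack of efficacy. The assay that the protocol provides to establish that cause is the one singled out for deferral. A patient who bleeds because neutralising antibodies have disabled the drug therefore looks, during dosing, like a patient who is under-dosed. The default for an under-dosed patient is escalation. The protocol accepts in section 18.1 that antibodies might inhibit the drug's function, and item 8 is its stopping rule for that case.

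At stake is the timing of an efficacy stop and possibly unnecessary dose increases for an individual patient. No sample-size, power or error-rate figure is involved.

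**Working it through.** **Does a scheduled neutralising result fall within dosing on any reading of end of trial?**

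Inputs from section 7: first patient first treatment 30-Aug-2017, last patient first visit 16-Dec-2017, LPLV 11-Sep-2019. Visit 2 is 14–21 days after visit 1 (section 8.1.9.1). Visit 2 is day 1, so visit 16 on day 533 is 532 days later.

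*Reading A, LPLV, nominal visit days.*
- First patient: 30-Aug-2017 + 532 days = 13-Feb-2019. From there to 11-Sep-2019 is 210 days = 30 weeks.
- Last patient: visit 2 falls between 30-Dec-2017 and 06-Jan-2018. Adding 532 days gives 15 to 22-Jun-2019, and LPLV is 88 to 81 days later.

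*Reading B, the patient's own visit 17.* Its window is minus 7 days, so days 582–589. Visits 4, 9 and 16 each have a window of ±7 days (sections 8.1.9.4, 8.1.9.5, 8.1.10.3).

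| Sample or dose | Day range | Wait to visit 17 (days) | Weeks |
|---|---|---|---|
| Last dose, visit 16 | 526–540 | 582−540 = 42 to 589−526 = 63 | 6–9 |
| Week-4 sample, visit 4 | 22–36 | 582−36 = 546 to 589−22 = 567 | 78–81 |
| Week-24 sample, visit 9 | 162–176 | 582−176 = 406 to 589−162 = 427 | 58–61 |

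On neither reading does a completing patient have a scheduled neutralising result during dosing. A patient who stops early has visit 17 eight weeks (minus up to 7 days) after his last dose (section 8.1.4), so the order is the same.

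**What happens meanwhile?** All patients start at 0.15 mg/kg (footnote to Figure 5–2). Without a neutralising result, the forced stop for bleeding is item 9. The minimum number of treated spontaneous bleeds before it applies is three per dose level. Counting from the start of the level at which the antibodies arise:

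- at 0.15 mg/kg: 3 + 3 + 3 = 9, with two escalations;
- at 0.20 mg/kg: 3 + 3 = 6, with one escalation;
- at 0.25 mg/kg: 3, with none.

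These are totals before item 9 applies, not bleeds avoided. Item 8 states no threshold. If it used the same three-bleed threshold, and the result were at hand at the third bleed, the two stops would differ by 9−3 = 6, 6−3 = 3 and 3−3 = 0 bleeds. Any delay in the result makes the difference smaller.

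**Would the existing batches be frequent enough?** Taking three months as 91 days from 30-Aug-2017, 532/91 gives 5 batches before the first patient's planned last dose. From 30-Aug-2017 to 15-Jun-2019 is 654 days, and 654/91 gives 7 before the last patient's. A sample waits 0–13 weeks for its batch, which is about as long as the 12-week escalation window. Batching alone would often be too slow, so testing on suspicion is needed as well.

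**The case against.** The strongest reply is that item 8 remains usable. It names no assay. Section 8.5 says: "Laboratory reports listing results from centrally analysed samples will be made available for the investigator". The parameters it lists there include free TFPI, concizumab concentration and binding antibodies, from which an investigator might infer the cause. The promise to notify investigators has little purpose unless a result can arrive in time to act on. The trigger list in footnote m is open. The DMC sees batched antibody results, can review ad hoc and recommend modification (section 12.8.2), and the sponsor's safety committee acts on its advice. The end-of-trial sentence may describe only the formal analysis and report, although the word analysed weakens that reading.

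Much of this stands. A reader might infer that the timing sentence makes item 8 impossible to apply. The protocol does not support that, because ad hoc testing or clinical judgement could still trigger it. What survives is narrower. No such route schedules a neutralising result during dosing, none is linked to item 8, and loss of efficacy is not a named trigger for testing.

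Sections 8.5 and 8.5.3 say that antibody results are often analysed, or are analysed, after LPLV. They lend only weak support, since both concern review in relation to adverse events. They do disagree with each other and with the in-trial batches in 8.5.2.7.

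The clinical consequence is also limited. Escalation needs the investigator's safety judgement, breakthrough bleeds are treated with FVIII, the patient may withdraw at any time, and item 9 stops treatment at the top dose.

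**Conclusion.** The point holds as an internal mismatch: a mandatory stopping criterion has no scheduled result to support it while the patient is dosed. That conclusion needs no assumption about which meaning of end of trial was intended. The likely effect is a later stop and up to two escalations for a patient whose neutralising antibodies arise at 0.15 mg/kg, up to one at 0.20 mg/kg, and possibly no effect at 0.25 mg/kg.

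Few patients, if any, would be affected: 33 are planned to be dosed, and section 18.1 reports no antibodies towards concizumab in clinical trials so far.

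Two further inferences should be resisted. Waits of 58–81 weeks describe a stored sample, not a patient left bleeding that long. And item 8 concerns efficacy; the safety stops for anaphylaxis, thromboembolism and DIC (items 4–6) do not depend on this assay.

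The LPLV intervals rest on planned dates and nominal visit days. The bleed difference of 6, 3 and 0 rests on an assumed threshold and an immediate result. The body of the flow chart (Table 2-1) could not be read here; section 8.5.2.7 cites it for the binding analysis and states the neutralising timing separately. The mismatch is worth correcting because the remedy is cheap, not because the expected harm is large.

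**What to change.** - In section 8.5.2.7, run the neutralising assay on confirmed binding-positive samples with the existing batches of about three months, and promptly when loss of efficacy is suspected in an antibody-positive patient.
- Release the result to the investigator and the DMC during treatment, give the notification sentence a time frame, and refer it to section 6.4 item 8.
- Add suspected loss of efficacy, and the neutralising assay, to footnote m of Table 2-2.
- Align the timing sentences in sections 8.5, 8.5.2.7 and 8.5.3.

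The assay is already planned and would run only on confirmed positives, so this changes its timing and some protocol wording. The cost is a few repeated runs and the transfer of samples during the trial from the specialised laboratory to the sponsor.

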8.5.2.8 Concizumab ELISA

Concizumab ELISA will be performed at all visits except at screening and at visit 3. Samples will be collected pre-dose at visit 2, 9 and 16.

Concizumab will be quantified using a validated ELISA assay. Recombinant human TFPI will be used to capture concizumab. A colorimetric detection signal is obtained by the enzymatic reaction of horseradish peroxidase labelled anti-human IgG4 specific antibodies with the chromogenic substrate TMB (3,3',5,5'-tetramethylbenzidine). The amount of anti-TFPI present in the calibration, quality control and test samples correlates with the obtained signal strength.

Validation of the assay follows current guidelines for bioanalytical method validation. Bioanalytical data will be reported in a bioanalytical report.

8.5.2.9 Total TFPI

Total TFPI ELISA sampling will be performed at all visits except at visit 3. Samples will be collected pre-dose at visit 2, 9 and 16.

The Total TFPI ELISA is included as an exploratory PD assessment.

The total TFPI level (free and concizumab bound) will be included as an exploratory biomarker assessment. The assay is an ELISA, where TFPI is captured by polyclonal anti-TFPI antibody, distanced from the binding site of concizumab, meaning that both free TFPI and concizumab bound TFPI will be captured. Detection will be obtained with a monoclonal antibody against TFPI, which does not bind to the concizumab epitope. Data will be reported in ng/mL TFPI.

Total TFPI ELISA will be performed at all visits, except visit 3. Sample will be collected pre-dose at visit 2.

Data will be reported in mg/ml TFPI

8.5.3 Human biosamples

If patient permission is obtained, plasma, serum and/or DNA for genotyping samples are to be taken for long term retention. The blood samples can be stored up to 15 years, for future potential exploratory purposes please refer to section [24.2](#).

Antibody samples storage and retention see section [24.2.1](#). The investigator is not able to review the results of antibody measurements in relation to AEs as these are analysed after LPLV.

Protocol
 Trial ID:NN7415-4255
 UTN:U1111-1179-3872
 EudraCT no.:2016-000614-29

~~CONFIDENTIAL~~

Date: 05 May 2017
 Version: 2
 Status: Final
 Page: 69 of 124

Novo Nordisk

If applicable, samples will be collected at visit 1 and at visit 17.

